12.3.3. Significant Adverse Events

Significant Adverse Events are those that are symptomatic and warrant discontinuation (temporary or permanent) of contact lens wear (excluding serious adverse events noted above). They include, but are not limited to:

- **Peripheral and non-infectious corneal ulcer:** Inflammatory reaction of the cornea characterised by peripheral or mid-peripheral corneal infiltrate with necrosis of the anterior stroma and excavation of the corneal epithelium. Bowman's layer is intact. Symptoms include moderate to severe pain, foreign body sensation, irritation, redness and tearing.
- **Acute red eye:** Inflammatory reaction of the cornea characterised by small, focal and diffuse corneal infiltration with minimal or no epithelial involvement. Symptoms include irritation, pain, redness, tearing, and photophobia.
- **Infiltrative keratitis:** Inflammatory reaction of the cornea characterised by anterior stromal infiltrates with or without epithelial involvement. Symptoms include mild to moderate irritation, and redness. Staining may be slight to moderate.
- **Conjunctivitis:** Inflammatory reaction of the conjunctiva characterised by discharge, grittiness, redness and swelling.
- **Contact Lens Induced Papillary Conjunctivitis:** Inflammatory reaction of the palpebral conjunctiva characterised by raised, swollen papillae.
- **Corneal Erosion:** Full thickness epithelial loss over a discrete area.
- **Superior Epithelial Arcuate Lesion:** Mechanical injury to the cornea characterised by an arc-like lesion in the periphery of the superior cornea.

12.3.4. Non-Significant Adverse Events

Non-significant Adverse Events are those that do not warrant discontinuation of contact lens wear, but may cause a reduction in wear time. Treatment, if needed, is usually with over the counter products. They include, but are not limited to:

- asymptomatic infiltrative keratitis
- blepharitis
- meibomitis
- contact dermatitis
- localised allergic reactions.

12.3.5. Unanticipated Adverse Device Events

Adverse device events or serious adverse device events are considered “unexpected” or “unanticipated” if they do not appear listed in the device technical manuals to date. These events require expedited reporting.

12.3.6. Event Severity

Events should be rated by a study investigator according to their severity:

- Mild:** No treatment required
Moderate: Treatment required. May involve temporary interruption of contact lens wear.
Severe: Requires referral to and treatment by an ophthalmologist.

12.4. Reporting

In the event of persistent irritation, redness, reduced visual acuity or any other unusual signs or symptoms, the participants will be advised to remove their lenses immediately.

Non-serious and anticipated device-related adverse events and adverse events should be recorded as part of Good Clinical Practice. Sponsors are expected to maintain up-to-date tabulations and/or line listings of all adverse device events.

All Serious Adverse Events should be reported to the HREC as per their reporting requirements. This should be followed by a more detailed written report commenting on potential confounding factors, results of investigations, treatment required and outcome. The Sponsor(s) and the Principal Investigator should review the events in conjunction with the known information about the device, and make a determination as to whether the event is device-related or not.

12.4.1. Expedited Reporting

UNSW, via the Principal Investigator (PI) of the clinical trial is required to report to the Therapeutic Goods Administration (TGA) single cases of serious and unanticipated device related adverse events.

- **Fatal or life-threatening unexpected adverse events** – the TGA should be notified as soon as possible but no later than 7 calendar days after first knowledge by the PI that the case qualifies, followed by a complete report as possible within eight additional calendar days.
- **All other serious, unexpected adverse events** – TGA notification as soon as possible but no later than 15 calendar days after first knowledge by the PI that the case meets the minimum criteria for expedited reporting.

In the case of an unexpected and serious adverse event that occurs outside Australia with use of the same product, the TGA and HREC should also be

notified. The time frame for this reporting should be within 72 hours of any significant safety issue which has arisen from an analysis of overseas reports or action which has been taken by another country's regulatory agency. This advice must include the basis for such action. Investigators should also be notified, who must in turn notify the HREC.

Reports should be on the 'Medical Device Incident Report Form' located on the TGA website (http://www.tga.gov.au/docs/html/forms/iris_mdir.htm) or similar format, and clearly marked 'Clinical Trial Adverse Device Event' and sent to:

The Medical Officer
Office of Devices, Blood and Tissues
Therapeutic Goods Administration
[name]
[name]

12.4.2. Foreseeable Adverse Events and Adverse Device Events

Risks associated with the use of the study lenses include:

- Eye discomfort (<1%)
- Eye redness (<1%)
- Blurry vision (<10%)
- Headaches (<10%)

12.4.3. Other Observations

There may be other situations that may necessitate rapid communication to regulatory authorities. Scientific and medical judgment should be applied for each situation. In general, information that might materially influence the benefit-risk assessment of a product or that would be sufficient to consider changes in product administration or in the overall conduct of a clinical investigation represent such situations.

12.5. Follow-up

Participants who experience an adverse response will be discontinued from the study and followed up until the condition resolves or the participant is referred to another practitioner.

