7.2. Participant Withdrawal

Participants may be permanently discontinued from the clinical trial for any of the following reasons:

- If, in the Investigator's opinion, it is in the best interest of the participant;
- Persistent clinical trial-related symptoms/complaints that are not correctable;
- Has a serious adverse event/serious adverse device event that is eye/lens related and/or which, in the Investigator's opinion, requires withdrawal of the participant;
- Participant voluntarily withdraws consent from the clinical trial (i.e. Revocation of Consent);
- If a participant is not compliant with the clinical trial requirements and instructions;
- Protocol violations/deviations.

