12.3. Definitions

12.3.1. Adverse Events

Adverse Event: Any undesirable clinical occurrence in a participant, whether it is considered to be device-related or not, that includes a clinical sign, symptom or condition and/or observation of an unintended technical performance or performance outcome of the device.

Adverse Events may be classified as Serious, Significant, Non-significant or Unanticipated as defined further on.

Adverse Device Event: A clinical sign, symptom or condition that is causally related to the device or the performance of the device system.

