13.1.3. Analysis

Participants who complete the study treatment will be included in the analysis dataset. Reasons and frequency distribution of participants discontinued will be reported.

Overall contamination rates, expressed as a binary variable, and contamination rates for type of organism will be compared between the worn contact lenses extracted from the two different types of lens packaging, as

well as between the hydrogel and silicone hydrogel lens materials extracted from the two different types of lens packaging.

Data will be summarised as means \pm standard deviations for variables measured on an interval scale and median \pm inter-quartile range for ordinal variables. Statistical tests will be employed to determine significant differences between the worn contact lenses extracted from the two different types of packaging. Commonly used tests of significance at each visit may include paired t-tests and group t-test for parametric data and Wilcoxon sign rank test and rank sum test for non-parametric data.

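### Sections 12.5 and 7.2 give different rules for discontinuation after an adverse response, and the completers-only dataset in 13.1.3, read plainly, drops lens pairs already collected

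*Combined protocol and SAP*

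**What the plan says.** Section 12.5 (Follow-up) is mandatory: "Participants who experience an adverse response will be discontinued from the study". The term adverse response is not defined there or in section 12.3. The nearest defined term, adverse event in 12.3.1, is broad: "Any undesirable clinical occurrence in a participant, whether it is considered to be device-related or not".

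Section 7.2 (Participant Withdrawal) is permissive: "Participants may be permanently discontinued from the clinical trial for any of the following reasons". Its adverse-event item reads: "Has a serious adverse event/serious adverse device event that is eye/lens related and/or which, in the Investigator's opinion, requires withdrawal of the participant". Other items cover the participant's best interest in the investigator's opinion and persistent study-related symptoms that cannot be corrected.

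Section 13.1.3 (Analysis) sets the dataset: "Participants who complete the study treatment will be included in the analysis dataset". For discontinued participants it promises only reasons and frequencies. Section 13.3 says that a missing data point is excluded only from analyses of that variable, and that a participant's visit data are kept when some observations are missing. It does not mention discontinued participants.

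**The concern.** For a minor event, 7.2 leaves a choice and 12.5 does not. Two investigators could therefore treat the same participant differently and each point to a section of the protocol. That is a matter of clinical conduct, but 13.1.3 carries it into the statistics: whoever is discontinued before completing is, on the plain reading, out of the analysis.

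The packaging comparison does not need the participant to finish the study. Under section 6 and Table 5, both lenses are worn for 45 minutes at the same visit, and packaging type is randomised between eyes at visits 1 and 2. Visit 3 compares two lenses that both come from Smart Touch packs. A participant who stops after visit 2 has already given every packaging pair that the design asks for.

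Two things are at stake. Valid pairs may be thrown away in a small preliminary study whose results are meant to size the next one. Inclusion may also depend on something related to the outcome: section 4.1 suggests that less microbial transfer may mean fewer adverse events and less redness.

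**Working it through.** **The sections side by side**

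| Section | Trigger | Force |
|---|---|---|
| 12.5 | Any adverse response (undefined) | Mandatory |
| 7.2, adverse-event item | Serious event that is eye- or lens-related and/or judged to require withdrawal | Permissive |
| 12.3.4 | Non-significant event | Does not warrant stopping lens wear |
| 12.3.6 | Mild: no treatment. Moderate: treatment, possibly a temporary break in wear | Severity grading only |

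The direct difference is between the first two rows. Sections 12.3.4 and 12.3.6 concern lens wear and treatment, not study participation, so they are context only.

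**The plan's own figure.** Section 13.1.1 asks for 25 participants to complete. It calls this an estimate and gives no effect size, power or dropout rate, so the figure can be neither reproduced nor refuted.

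**Inputs for the size.** Section 12.4.2 lists eye discomfort <1%, eye redness <1%, blurry vision <10% and headaches <10%. All are ceilings. The section does not say whether they are per participant or per visit, so both readings are shown. Section 6 gives three visits. Independence between events and visits is my assumption.

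**Events that fit the selection argument (redness, discomfort)**
- Per participant: 1 − 0.99² = 0.0199; × 25 = 0.5.
- Per visit, three visits: 1 − 0.99⁶ = 0.0585; × 25 = 1.5.

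**All four listed events**
- Per participant: 1 − 0.99² × 0.90² = 1 − 0.7939 = 0.206; × 25 = 5.2.
- Per visit, three visits: 1 − 0.7939³ = 0.500; × 25 = 12.5.

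Independence matters little on the per-participant reading. If the events never coincided, the ceilings would simply add: 0.02 × 25 = 0.5 and 0.22 × 25 = 5.5.

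**Comparison with 7.2.** Under its adverse-event item, none of the four listed events by itself forces removal, so the corresponding loss is 0 unless the investigator judges otherwise.

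**What the counts mean.** They count participants who could be discontinued, not lost pairs. Someone stopped at visit 1 before lens collection loses nothing that could have been analysed. Someone stopped after visit 2 has two packaging pairs at risk.

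**The case against.** The other side has several good points.

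- **The sections can be followed together.** A reader might infer that 12.5, 7.2 and 12.3.4 are mutually exclusive. They are not. Section 7.2 only permits, and its first item is the investigator's opinion, so a site applying 12.5 breaches nothing in 7.2. Section 12.3.4 concerns stopping lens wear. What remains is that 12.5 removes a discretion that 7.2 grants, on an undefined trigger.
- **Adverse response may be narrower than adverse event.** The rest of the sentence in 12.5 speaks of follow-up until a condition resolves or the participant is referred, which could mean a condition needing care rather than a passing headache. That reading is possible, but the protocol does not state it.
- **The larger counts do not support a selection effect.** A reader might take 5 or 12.5 of 25 as the scale of bias. Section 4.2.1 ties headache to visual fatigue with the low-power lenses and calls it unlikely, and every study lens has the same power. Nothing in the documents links headache or blurred vision to contamination.
- **25 is a completer target.** The documents do not say that losses would go unreplaced, so a smaller final sample cannot be inferred. Replacement would restore the number but would not undo selection.
- **The arms cannot become unbalanced.** A discontinued participant takes both lenses of each pair out, so differential loss between packaging types does not arise.
- **Exclusion of earlier pairs is a reading, not a certainty.** Completing the study treatment is undefined. Tests are described at each visit, visit 3 has its own consent in Table 5, and sections 5.1 and 7.3 still speak of two visits. A visit-wise reading, helped by 13.3, would keep the earlier pairs. This stands, but 13.3 addresses missing observations and not discontinued participants, so the choice could still be made after the results are known.

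**Conclusion.** The point holds in a limited form. Section 12.5 is mandatory on an undefined trigger, while 7.2 is permissive and centred on serious events and judgement; the two need to be reconciled. Section 13.1.3, read plainly, then leaves out complete pairs already collected from discontinued participants, and 13.3 does not clearly prevent this.

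The consequence is wasted valid pairs and possible selection on contamination, not imbalance between packaging types. Selection depends on adverse responses being related to contamination. Section 4.1 offers this only as a potential benefit, and the documents do not establish it for 45 minutes of wear.

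For the events that fit that argument, the ceiling is about 0.5 of 25 participants, or about 1.5 if the rates apply at each of three visits. With headache and blurred vision added, the ceiling for waste is about 5 of 25 per participant. The per-visit figure of 12.5 rests on a reading that 12.4.2 does not state. All of these are upper limits, and the actual loss may be small. The change is still worth making because it costs almost nothing.

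**What to change.** 1. The sponsor and the investigator should reconcile 12.5 with 7.2 so that one rule governs discontinuation, and should define adverse response or replace it with a defined term. This review takes no position on which rule is right.
2. Section 13.1.3 should define the analysis set by visit. Every lens pair validly collected before discontinuation is analysed, except where a participant withdraws consent to use of the data.
3. An analysis restricted to participants who complete all visits should be named as a sensitivity check, with completion defined.

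The cost is a few sentences of protocol text and one extra analysis; no further data are collected. The downside is slightly unequal numbers of pairs across visits, so comparisons that span visits must state which participants contribute.

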13. STATISTICS

13.1. Description

Data stored in relational databases will be imported into SPSS software for statistical purposes. Statistical analysis will initially be reported in Excel. Data will be investigated for quality using range checks and frequency distribution. Underlying distributions of variables will be tested. Details of statistical analysis are described in Section 13.1.3.

13.1.1. Number of Participants

25 participants will be required to complete the study.

This sample size is an estimate for this preliminary study, to determine whether differences in microbial contamination rates on the back surface of worn soft contact lenses can be detected.

The results of this study will be used to inform the detection limits for microbial contamination rates on the back surface of worn soft contact lenses between the two different types of lens packaging. This will assist to determine the appropriate sample size required to conduct a longer-term dispensing study.

13.1.2. Significance

A p-value less than or equal to 5% will be considered to be statistically significant.

13.1.3. Analysis

Participants who complete the study treatment will be included in the analysis dataset. Reasons and frequency distribution of participants discontinued will be reported.

Overall contamination rates, expressed as a binary variable, and contamination rates for type of organism will be compared between the worn contact lenses extracted from the two different types of lens packaging, as

well as between the hydrogel and silicone hydrogel lens materials extracted from the two different types of lens packaging.

Data will be summarised as means \pm standard deviations for variables measured on an interval scale and median \pm inter-quartile range for ordinal variables. Statistical tests will be employed to determine significant differences between the worn contact lenses extracted from the two different types of packaging. Commonly used tests of significance at each visit may include paired t-tests and group t-test for parametric data and Wilcoxon sign rank test and rank sum test for non-parametric data.

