5. TRIAL OBJECTIVES AND CLINICAL HYPOTHESIS

5.1. *Trial Objective*

The objective of this study is to investigate the microbial contamination rates on the back surface of hydrogel and silicone hydrogel contact lenses extracted from Smart Touch Technology blister packs versus conventional lens packaging, and the impact of EDTA in the packaging solution after short-term placement on the eye (45 minutes), in a randomized, contralateral, investigator-masked non-dispensing study comprising of two visits.

5.2. *Clinical Hypothesis*

The microbial contamination rates on the back surface of soft contact lenses extracted from Smart Touch Technology blister packs will be lower compared to the microbial contamination rates on the back surface of contact lenses extracted from conventional lens packaging.

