6. TRIAL DESIGN

This will be a prospective, single centre, randomized, contralateral, investigator-masked non-dispensing study. This study requires three visits of approx. 1 hour duration each.

At the first visit, if possible, the order in which the hydrogel and silicone hydrogel contact lenses are allocated to the study participants will be randomized. At the second visit, participants will be crossed over to the alternate lens type (hydrogel or silicone hydrogel).

At each visit, participants will be instructed to:

- Wash their hands prior to handling the contact lenses;
- Swab their thumb and two index fingers of the hand routinely used to conduct contact lens insertion using a sterile cotton swab moistened with sterile preservative free saline for the evaluation of skin microbiota;
- Follow the manufacturer's guidelines for lens insertion;
- Open the blister pack and insert the contact lens randomly assigned for the right eye;
- Open the blister pack and insert the contact lens assigned for the left eye;
- Contact lenses will be removed aseptically by a masked investigator wearing sterile latex gloves, who is experienced in this technique, after 45 minutes of lens wear. All contact between the contact lens with the eyelids and eyelashes during lens removal will be avoided.

Lenses and finger swabs will be analysed for microbial contamination using established routine microbiology protocols. The number and species of organisms will be determined.

A minimum washout period of 48 hours will occur between the two study visits.

All proposed procedures conform to the NHMRC Statement on Human Experimentation.

Participants are considered enrolled when they have signed the informed consent form and are regarded as part of the clinical trial population.

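### Organism-type comparisons fall under the general 5% rule with no list, adjustment or exploratory label, so the chance of a false single-organism finding is not controlled

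*Combined protocol and SAP*

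**What the plan says.** Section 13.1.3 (Analysis) sets out two layers of outcome: "Overall contamination rates, expressed as a binary variable, and contamination rates for type of organism will be compared" between the two packaging types. For the second layer, the wording is that "contamination rates for type of organism will be compared between the worn contact lenses extracted from the two different types of lens packaging". The same sentence adds a second contrast, as "well as between the hydrogel and silicone hydrogel lens materials extracted from the two different types of lens packaging". The tests are left open: "Commonly used tests of significance at each visit may include paired t-tests and group t-test for parametric data", with the Wilcoxon signed-rank and rank-sum tests as the non-parametric options. No test for paired binary data is named.

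Section 13.1.2 (Significance) gives the only decision rule: "A p-value less than or equal to 5% will be considered to be statistically significant". It is not tied to any endpoint or contrast.

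Section 6 (Trial Design) says of the cultures: "The number and species of organisms will be determined". No section says how many organism types are expected or how they will be grouped.

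Section 6.2 names one primary endpoint, the contamination rate of the back lens surface, without saying whether that is the overall rate or the rate by organism. On size, section 13.1.1 says "25 participants will be required to complete the study" and calls the figure an estimate for a preliminary study.

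**The concern.** Read together, sections 13.1.2 and 13.1.3 let each organism type be compared at the same 5% level as the overall rate. If types are counted at species level, the number of comparisons depends on what grows and is known only after the cultures are read. The material contrast and testing at each visit add further comparisons.

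At stake is how a scattered result is read. Suppose the overall rate shows no packaging difference, but one organism appears on four conventional lenses and on no Smart Touch lens. Nothing in the plan stops that from being reported as significant in the same sense as the overall comparison. The clinical hypothesis in section 5.2 is directional (Smart Touch rates "will be lower compared to the microbial contamination rates on the back surface of contact lenses extracted from conventional lens packaging"), so a chance difference in that direction would look like support for it. It could also be carried into the sample-size calculation for the later dispensing study.

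**Working it through.** **Inputs from the documents**
- Threshold: 0.05 per test (13.1.2). Sidedness is not stated; two-sided tests are assumed.
- Pairs: 25 (13.1.1).
- Candidate tests: paired t and signed-rank (13.1.3). Exact McNemar is added for comparison because the outcome is binary and paired.

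**Inputs assumed, because the documents do not give them**
- Number of tests: 10, for example 5 organism types in each of 2 materials; 20 as a sensitivity case.
- Discordance D, the share of pairs in which the organism is on one lens only: 4%, 10% or 20%. In 25 pairs that is 1, 2.5 or 5 discordant pairs on average.
- Independence between tests.

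**The plan's own figures.** The 25 cannot be reproduced, since no rate, difference or power is given. One test at 0.05 has a nominal error of 5%.

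**Step 1: nominal error over k tests.** The formula is 1 − (1 − 0.05)^k. It gives 22.6% for k = 5, 40.1% for k = 10, 48.7% for k = 13, 51.2% for k = 14 and 64.2% for k = 20. Even with full-size tests, at least 14 are needed before a false positive is more likely than not.

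**Step 2: what one organism needs to reach p ≤ 0.05.** Take a 4–0 split in 25 pairs.
- Paired t: mean difference 4/25 = 0.16; variance (4 − 16/25)/24 = 0.14; t = 0.16/√(0.14/25) = 2.14 on 24 df; p = 0.043.
- Signed-rank, normal approximation: z = 4/√4 = 2; p = 0.046.
- Exact McNemar: p = 2 × 0.5^4 = 0.125. A 5–0 split gives 0.0625; the first significant one-way split is 6–0, with 2 × 0.5^6 = 0.031.

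**Step 3: actual size per test.** Under no difference, each pair falls in either discordant cell with probability D/2. Summing the multinomial probabilities of all splits with p ≤ 0.05 gives the size a, and the chance of at least one false positive is 1 − (1 − a)^k.

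| D | Test | a | k = 10 | k = 20 |
|---|---|---|---|---|
| 4% | paired t / signed-rank | 0.0019 | 1.9% | 3.7% |
| 10% | paired t / signed-rank | 0.0223 | 20% | 36% |
| 20% | paired t / signed-rank | 0.0485 | 39% | 63% |
| 10% | exact McNemar | 0.0009 | 0.9% | 1.8% |
| 20% | exact McNemar | 0.0088 | 8.5% | 16% |

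The result is driven by three things the plan leaves open: how many types are tested, how common each is, and which test is used.

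**The case against.** The strongest reply is that the risk may be small. Organisms found on very few lenses can hardly reach significance in 25 pairs, and with an exact paired test ten comparisons stay below 10% even at 20% discordance. Part of the larger figures comes from applying a t or normal-approximation test to sparse 0/1 data, which is a separate issue from multiplicity. This stands, and it is why no single figure can be quoted. It does not remove the gap, because the exact test is not among those the plan names.

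It can also be said that 13.1.3 only says organism rates will be compared, and that its sentence on statistical tests does not mention organisms. Testing each of them at 5% is therefore an inference. It is the natural one, since 13.1.2 carries no restriction, but it is not written out. The types might also be reported in a few broad groups, which would limit the count.

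Two stronger readings are tempting. A reader might infer that a chance organism finding is likely. The documents do not support that: 10 tests give 2% to 39% with the named tests, and passing even odds takes at least 14 independent tests at full size. A reader might also infer that one significant organism would establish a benefit under the plan. It would not: 13.1.2 defines when a result is called significant, and the plan has no success criterion. Section 13.1.1 describes the study as preliminary and as informing a later one. That lowers the consequence but does not replace an exploratory label.

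**Conclusion.** The concern holds as a matter of control. Organism-type comparisons share the 5% rule with the overall rate and are not enumerated, adjusted or labelled, so the chance of a false single-organism result has no stated limit. Its size is undetermined by the documents. The range of about 2% to 39% for the named tests, and about 1% to 9% for exact McNemar at 10% to 20% discordance, rests on ten independent two-sided tests on 25 pairs with equal discordance for every type. Positive correlation between organisms on the same lens would generally lower these figures; more types would raise them. Severity is minor, given the preliminary purpose of the study.

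**What to change.** Add one sentence to 13.1.3: comparisons by type of organism are exploratory and are reported as counts and paired differences with 95% intervals, without a statement of significance. If p-values are wanted, the sentence should instead require Holm adjustment across organism types within each contrast. With 5 types, for instance, the smallest p-value would have to be at or below 0.05/5 = 0.01, so a 4–0 split (p = 0.043 by paired t) would no longer count. Holm used this way controls error within a contrast, not across contrasts.

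Leave the 5% rule in place for the overall-rate comparisons: packaging, EDTA (part of the primary objective in the synopsis), lens material, and hand swab against lens (section 6.3). Restricting the rule to the packaging contrast alone would remove significance testing from the other three, which this point does not require.

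The cost is one sentence and no extra data or participants. What is given up is a stand-alone significance claim for a single organism or, under Holm, the unadjusted threshold for one.
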